3.4.1 Reasons for Discontinuation

The reason for withdrawal must be determined by the Investigator and recorded in the subject's medical record and on the eCRF. If a subject is withdrawn for more than one reason, each reason should be documented in the source document and the most clinically relevant reason should be entered on the eCRF.

If an adverse event (AE) is a reason for discontinuation, then "Adverse event" must be recorded as the reason for discontinuation on the eCRF.

Reasons for discontinuation include but are not limited to:

- Adverse event
- Protocol violation
- Withdrawal by subject
- Lost to follow-up
- Lack of efficacy
- Investigator decision

3.4.2 Subjects 'Lost to Follow-up' Prior to Last Scheduled Visit

At least three documented attempts must be made to contact any subject lost to follow-up at any time point prior to the last scheduled contact (office visit or telephone contact). One of these documented attempts must include a written communication sent to the subject's last known address via courier or mail (with an acknowledgment of receipt request) asking that they return any unused investigational product (if applicable) and return to the site for final safety evaluations.

4. PRIOR AND CONCOMITANT TREATMENT

4.1 Prior Treatment

Prior treatment includes all treatment (including herbal treatments, vitamins, nonpharmacological treatment such as psychotherapy as appropriate) received within 30 days (or the pharmacokinetic equivalent of 5 half-lives, whichever is longer) of and discontinued prior to the date of the first dose of investigational product. Prior treatment information must be recorded on the appropriate eCRF page.

4.2 Concomitant Treatment

All subjects must be optimally managed on diuretics and oxygen therapy as indicated by the standard of care.

Medication or treatment for heart failure or respiratory disease must be maintained during the trial, unless contraindicated.

4.3 Allocation of Subjects to Treatment

This is an Open-Label extension of the parent study. All patients who enroll into this study received an open-label levosimendan. With the availability of oral levosimendan capsules, all consenting patients in TNX-LVO-05 will be transitioned to daily doses of oral levosimendan and continue in the study for 3 years following transition to oral levosimendan or termination of the trial by the patient or physician decision.

5. INVESTIGATIONAL PRODUCT

5.1 Levosimendan

IV Levosimendan

Levosimendan will be provided to the subjects by the sponsor as a sterile clear, yellow to orange solution in clear glass vials. Each vial contains a 5 mL volume and is intended for a single use. Levosimendan is supplied at 2.5 mg/mL (12.5 mg/5 mL) and includes levosimendan, povidone, citric acid and ethanol. Additional information is provided in the Simdax (levosimendan) injection Investigator's Brochure and SmPC.

Oral Levosimendan

Oral levosimendan will be provided as a single-unit, immediate release, size 3, yellow and grey capsule. Each capsule contains 1mg levosimendan, intended to be released rapidly for absorption from the gastrointestinal tract. In addition to active ingredient, the capsules contain the following excipients, all of which comply with the monographs of the European Pharmacopoeia.

Levosimendan is supplied by the Orion Corporation, Espoo, Finland.

5.2 Packaging

IV Levosimendan

Levosimendan will be provided in sterile, single-use clear rubber-stoppered glass vials. Details on the packaging of study drug will be provided in the study manual.

Oral Levosimendan

Levosimendan will be provided in high-density polyethylene (HDPE)-container closed with HDPE/poly propylene (PP) screw closure.

5.3 Labeling

Study drug labels will contain information to meet the applicable regulatory requirements.

Each container will have appropriate directions for use and other required information.

Drug accountability forms will be used for tracking study drug administration. Information from the container will be included on the subject's drug accountability form to document capsule usage.

5.4 IV Levosimendan (Weekly Infusions)

5.4.1 Dosage and Administration

During the routine weekly infusion, patients will be administered a continuous intravenous (IV) infusion of a standard infusion dose of 0.075 - 0.1 µg/kg/min for 24 hours (±30 min); (levosimendan). The dose may be adjusted by the treating physician as needed (see section 6.4.2). No bolus of study drug will be administered.

Study drug concentrated solution (2.5 mg/mL), levosimendan, will be mixed with diluent and administered as weekly infusions at 0.075 µg/kg/min for 24 hrs. Patients may have a dose escalation at Weeks 3 at a rate of 0.10 µg/kg/min for 24 hrs, unless there has been a meaningful change in blood pressure or heart rate ([Attachment 4](#)) or other prohibitive rationale.

If a subject was down-titrated to 0.05 µg/kg/min in the TNX-LVO-04 study for either the Lead-In or during the double-blind portion of the study, the subject should start at this dose, with the first opportunity to up-titrate at Week 3 of the Open-Label Extension Study, TNX-LVO-05.

Note: A patient will be discontinued from the study, if the patient develops a complication or infection associated with the PICC line or port-a-cath that prevents its further use.

The infusion rate of study drug may be decreased, interrupted, or discontinued for safety reasons, according to the discretion of the investigator, as described in the following sections.

To prevent possible medication errors or miscalculations, refer to Attachment 4 of this protocol before administration of study drug to calculate the appropriate infusion rate based on the subject's body weight.

The diluted infusion is administered intravenously by a peripheral or central route. No other treatments should be administered via the same line.

The concentration of the diluted infusion is about 50 µg/mL in 5% Dextrose or 0.9% Normal Saline (12.5mg/255mL in a 250 mL bag; 25mg/510mL, 2 vials in a 500 mL bag).

The IV tubing should be primed to fill the volume to the IV entry site before starting the infusion.

5.4.2 Dose Adjustment

The infusion rate of study drug may be decreased or interrupted as clinically warranted if the subject has hypotension, tachycardia, or signs or symptoms consistent with hypovolemia (e.g., low SBP, decreasing urine output with rising blood urea nitrogen [BUN] and serum creatinine). Record the time of discontinuation or down titration. Patients should be monitored closely until clinically stable. See [Attachment 1](#) for infusion rates and instructions on dose adjustments.

Refer to the following subsections for additional guidance on events that require study drug discontinuation or dosage adjustment, permanent discontinuation, and re-initiating study drug in subjects in whom clinical stability has been restored. In the event of a dose interruption, the infusion should be extended the amount of time of the interruption, but no more than four hours.

5.4.3 Storage

Study drug (levosimendan infusion concentrate) must be stored between 2-8°C (35-46°F) in a temperature monitored refrigerator which can be locked and protected from light.

The Sponsor must be notified upon discovery of any excursion from the established range. Temperature excursions will require site investigation as to cause and remediation. Tenax will determine the ultimate impact of excursions on the investigational product and will provide supporting documentation as necessary. Under no circumstances should product be dispensed to subjects until the impact is determined and product is deemed appropriate for use.

5.5 Oral Levosimendan

5.5.1 Dosage and Administration

Dosing Regimen: Subjects will start with a 1 mg levosimendan dose (in the morning) for 2 weeks. If tolerated, the dose will be increased after 2 weeks to 1 mg BID, after 4 weeks to 1mg TID, and after 6 weeks (if applicable)¹ to 1mg QID. The titration sequence is as follows:

Previous IV Infusion	Week 0 (Office)	Week 2 (Home)	Week 4 (Home)	Final Visit Week 6 (Office)	Week 8 (Office)
----------------------	-----------------	---------------	---------------	-----------------------------	-----------------

0.10 µg/kg/min	1mg QD (1mg total daily dose) Morning	1mg BID (2mg total daily dose) Every 12 hrs.	1mg TID (3mg total daily dose) Every 8 hrs.	Patient evaluated for further titration (up or down) ¹	Only patients titrated (up or down) at Week 6 No further dose titration above 4mg QID
----------------	---	--	---	---	---

¹ At the investigator's discretion, patients that have not demonstrated an adequate response to drug therapy and a tolerance to the 1mg levosimendan TID may be titrated to 1mg QID. Patients that have not tolerated 1 mg levosimendan TID should be down titrated to 1mg BID. All patients that are titrated at Week 6 should return for a Week 8 visit.

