13.	APPENDICES.....	72
13.1	APPENDIX 1: Summary of Changes for Previous Protocol Amendments.....	72
14.	ATTACHMENTS	82
14.1	ATTACHMENT 1: Child Pugh Classification	83
14.2	ATTACHMENT 2: Kansas City Cardiomyopathy Questionnaire.....	84
14.3	ATTACHMENT 3: Cardiac Event Recommendations and Management	88
14.4	ATTACHMENT 4: Study Drug Dose and Dosing Table	89
14.5	ATTACHMENT 5: Patient Diary of Daily Heart Rate and Blood Pressure Readings	91

ABBREVIATIONS

6MWT/D	6-minute walk test/distance
AE	adverse event
ANCOVA	analysis of covariance
BA	bioavailability
BE	Bioequivalence
BID	Twice daily
BMI	body mass index
BUN	blood urea nitrogen
CABG	coronary artery bypass graft
CDER	Center for Drug Evaluation and Research
CFR	Code of Federal Regulations
CK	Creatine kinase
C _{max}	maximum plasma concentration
C _{min}	minimum plasma concentration
CRA	Clinical Research Associate
eCRF	Case Report Form
CRO	Contract Research Organization
eCRF	electronic case report form
eGRF	estimated glomerular filtration rate
ECG	electrocardiogram
EMA	European Medicines Agency
FDA	Food and Drug Administration
GCP	Good Clinical Practice
HCG	human chorionic gonadotropin
HFpEF	heart failure with preserved ejection fraction
HIPAA	Health Insurance Portability and Accountability Act
IB	Investigator's Brochure
ICH	International Conference on Harmonisation
IND	Investigational New Drug
IRB	Institutional Review Board
ITT	intention-to-treat
IV	intravenous
IWRS	Interactive Web Response System

LNH	Low, Normal, High
MedDRA	Medical Dictionary for Regulatory Activities
MHRA	Medicines and Healthcare Products Regulatory Agency (UK)
NDA	New Drug Application
PD	Pharmacodynamic
PH	Pulmonary hypertension
PK	pharmacokinetic
PP	per-protocol
QD	once daily
QID	Four times daily
QoL	quality of life
RBC	red blood cell
SAE	serious adverse event
SAP	Statistical Analysis Plan
SBP	Systolic blood pressure
SmPC	Summary of Product Characteristics
TAPSE	Tricuspid annular plane systolic excursion
TID	Three times daily
$t_{1/2}$	apparent terminal-phase disposition half-life
t_{max}	time to maximum plasma concentration
TMF	Trial Master File
WBC	white blood cell
λ_z	apparent terminal-phase disposition rate constant

STUDY SYNOPSIS

Sponsor/Company Tenax Therapeutics, Inc.				
Finished product: Oral levosimendan				
Active ingredient: (-)-(R)-[[4-(1,4,5,6-tetrahydro-4-methyl-6-oxo-3-pyridazinyl)phenyl]hydrazono]propanedinitrile				
Study code: TNX-LVO-05	Date: Version 4.1 04 June 2021			

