Body Weight	X	X					X	X
Serum Chemistry and Hematology (Local Lab) ⁷	X	X			X ⁶	X	X	X
Child Pugh Class ⁷	X							X
Vital Signs	X	X	X	X	X	X	X	X
Pharmacokinetic Sample		X ²		X	X ²	X ²		
Electrocardiogram (ECG)	X	X			X ⁶	X		X
Levosimendan Administration (oral) / Dose Titration ³		X	X	X	X ⁴			
NYHA Functional Class	X	X			X ⁶	X	X	X
6 - Minute Walk Test	X	X			X ⁶	X	X	X
Adverse Events/SAEs ⁸	X	X	X	X	X	X	X	X
Concomitant procedures and medications	X	X	X	X	X	X	X	X
KCCQ Assessment ⁹	X	X			X ⁶	X	X	X

Footnotes for Time and Events Schedule

1. Visits will be scheduled 7-9 days following completion of the levosimendan IV dose and every 14 days through the oral levosimendan transition (+/- 48 hrs); at the Investigator's discretion, Week 2 and 4 visits may be performed remotely.
2. Blood sample to be taken prior to the patient's daily dose of oral levosimendan.
3. The first dose of oral levosimendan to be taken 7-9 days after the patient's final weekly IV levosimendan dose. Once oral levosimendan begins, subjects must completely discontinue weekly levosimendan infusions. Patients will begin a daily dose regimen of 1mg daily and titrated at 1mg increments every 2 weeks, as tolerated.
4. At the investigator's discretion, patients that have not demonstrated an adequate response to drug therapy and a tolerance to the 1mg levosimendan TID may be titrated to 1mg QID. Patients that have not tolerated 1 mg levosimendan TID should be down titrated to 1mg BID. All patients that are titrated at Week 6 should return for a Week 8 visit.
5. Due to the COVID-19 pandemic, the investigator may have a phone conversation with the patient rather than having the patient come in for an office visit. The phone conversation should include the following, as reported by the patient; adverse events, concomitant medications (new or changed), concomitant procedures, and blood pressure & heart rate (use provided home blood pressure cuff).
6. If a patient is up or down titrated and therefore scheduled for a Week 8 visit, these procedures do not need to be performed at Week 6.
7. Local labs will be drawn (including NT-proBNP). Child-Pugh Class is only required for patients with documented liver disease.
8. During routine visits and throughout a participation in the study, patients should be queried for any new or changes to AEs, concomitant medications, concomitant procedures, hospitalizations, and/or emergency room visits

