1.3.8 Target Plasma Concentrations of OR-1896 in chronic treatment of PH-HFpEF Patients

Levosimendan represents an active prodrug to the active metabolite OR-1896 with extended pharmacodynamic effects that parallel those of levosimendan. The elimination half-life of levosimendan itself is short (approximately 1 hour), whereas that of the metabolite OR-1896 is long (70-80 hours in heart failure subjects). During a long-term oral dosing of levosimendan with constant daily dose, the OR-1896 plasma levels achieve a steady-state with minimal daily variation.

The chronically active moiety of levosimendan administration is the metabolite OR-1896. Levosimendan is cleared within 5 hours of ending an infusion.

The wide range of OR-1896 concentrations observed in daily oral levosimendan dosing (PERSIST study, see Section 1.3.4) and weekly IV administration (HELP Study, Section 1.3.5) precludes the identification of a specific oral dose to be used in the IV to oral transition. Importantly, the range of OR-1896 plasma concentrations observed in the PERSIST study of class IIIb-IV CHF patients overlap those observed in the HELP Study of PH-HFpEF patients (Figure 3).

[figure not shown]

Figure 3. Comparison of OR-1896 Plasma Concentrations in PERSIST Study of Daily Oral Levosimendan (1mg QD, 1 mg BID) versus the HELP Study of Weekly IV Levosimendan (0.1 ug/kg/min for 24 hrs).

However, only one third of the HELP Study patients were sampled at peak OR-1896 levels, 2-3 days following their previous levosimendan IV dose. The remaining patients were sampled beyond the period of peak OR-1896 concentrations observed in a weekly IV levosimendan regimen. An opportunity to titrate patients to 4 mg total daily dose (1mg QID), as tolerated based on blood pressure and heart rate, will ensure all transitioning patients will achieve adequate steady state levels of OR-1896.

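### The Week 8 cell of the oral titration table gives the dose ceiling as 4 mg QID, literally 16 mg/day; every other current statement puts it at 1 mg QID, or 4 mg/day

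*Protocol*

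**What the plan says.** Protocol 5.5.1 sets out the oral regimen in a sentence, a table and a footnote. The sentence starts patients on 1 mg in the morning and steps them through BID and TID to 1 mg QID where applicable. The table's dose cells for Weeks 0, 2 and 4 give the amount per intake, the frequency and, in brackets, the daily total. Week 2 is "1mg BID (2mg total daily dose") and Week 4 is "1mg TID (3mg total daily dose"). The Week 6 cell gives no dose and says only that the patient is assessed for titration up or down. The Week 8 cell applies to patients titrated at Week 6 and ends with "No further dose titration above 4mg QID". Footnote 1 to the table says that patients with an inadequate response and "tolerance to the 1mg levosimendan TID may be titrated to 1mg QID".

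Elsewhere, Section 1.3.8 speaks of the chance to "titrate patients to 4 mg total daily dose (1mg QID"). Section 2.5 and SAP 2.2.3 give the same maximum, and footnote 4 to the Time and Events Schedule repeats the table footnote. The synopsis and Section 1.3.8.3 state only a top daily dose of 4 mg.

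**The concern.** A maximum dose should have one value throughout a protocol. Here the dosing table, which sites are likely to consult first, carries a different figure from the text around it. The table's own format invites the literal reading: in each of the other dose cells the number before the frequency is the amount per intake. It is also the only cell in the table that states the top dose, so someone reading the table alone sees only the wrong figure.

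The figure bears on safety. Section 1.3.6 names hypotension and tachycardia as the main safety events of interest with this drug. The oral experience cited in the protocol is 1 and 2 mg/day in PERSIST (Section 1.3.4) and single doses of 1, 2 and 4 mg (Section 1.3.7). A literal 16 mg/day lies well outside both. Section 2.5 allows later capsule supplies to be shipped to the patient's home, and the patient diary (Attachment 5) leaves the number of capsules for the physician to fill in, so the diary prints no ceiling of its own.

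**Working it through.** **Inputs.** The dose cells come from the table in Protocol 5.5.1. The protocol's abbreviation list gives QID as "Four times daily", with TID three times, BID twice and QD once daily. Section 5.1 gives the capsule strength as 1 mg.

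**Formula.** Total daily dose = amount per intake × intakes per day.

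**Reproducing the plan's own totals first, then the ceiling:**

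| Where stated | Dose as written | Calculation | Daily total | Total printed in the plan |
|---|---|---|---|---|
| 5.5.1 table, Week 0 | 1 mg QD | 1 × 1 | 1 mg | 1 mg |
| 5.5.1 table, Week 2 | 1 mg BID | 1 × 2 | 2 mg | 2 mg |
| 5.5.1 table, Week 4 | 1 mg TID | 1 × 3 | 3 mg | 3 mg |
| 1.3.8, 2.5 and SAP 2.2.3 | 1 mg QID | 1 × 4 | 4 mg | 4 mg |
| 5.5.1 table, Week 8 | 4 mg QID | 4 × 4 | 16 mg | none |

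The formula returns every daily total that the plan prints. Only the Week 8 cell departs from the 4 mg maximum: 16 / 4 = 4 times the intended ceiling, or 16 capsules a day instead of 4.

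**Other current statements of the ceiling:**

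- 1 mg QID, six places: the sentence above the 5.5.1 table; footnote 1 to that table; Time and Events footnote 4; Section 1.3.8; Section 2.5; SAP 2.2.3. The last two each state it twice.
- 4 mg daily only, two places: the synopsis and Section 1.3.8.3.

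That makes 6 + 2 = 8 places against one cell. The amendment log in Appendix 1 mentions a 3 mg maximum, but that text is superseded and is not counted.

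**Could a patient reach 16 mg/day by following the protocol?**

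- The cell limits titration; it does not instruct any step.
- Under footnote 1, the only upward step at Week 6 is from 1 mg TID to 1 mg QID.
- Time and Events footnote 3 has doses "titrated at 1mg increments every 2 weeks, as tolerated".
- The schedule row headed "Levosimendan Administration (oral) / Dose Titration" is marked at Weeks 0, 2, 4 and 6 and is blank at Week 8.

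So 16 mg/day cannot be reached without departing from these rules.

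**The case against.** The strongest reply is that this is a slip of notation and not a second dosing rule. The authors probably ran the daily total and the schedule together. Section 2.5 does much the same at the 3 mg step, where it writes the daily total, the per-intake dose in brackets, and then TID again. The correct dose stands directly above and below the table, the remaining text agrees, and the titration rules never lead to 16 mg/day. Section 9.1.8 defines overdose against a prespecified total daily dose, and the only maximum labelled as a daily total is 4 mg. On this view it is an editorial correction of little weight, and one that protocol v5.0 may already contain.

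Most of that stands. The origin is very likely a merged shorthand, the intended dose is not in doubt, and the practical risk is low. It does not make the cell correct. Section 2.5 prints the per-intake dose beside its shorthand and the Week 8 cell does not, so nothing within the cell corrects the literal reading. Close agreement everywhere else shows what the cell should say; it is not a reason to leave a wrong maximum dose in the dosing table. Whether v5.0 still carries the error cannot be settled from the documents available.

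**Conclusion.** The concern holds. As written, the Week 8 cell states a ceiling of 16 mg/day where the intended ceiling is 4 mg/day, and it contradicts eight other places. The factor of 4 is the size of the misprint and not an exposure any patient is likely to have had. No endpoint, estimate or analysis depends on the cell, and the SAP plans no hypothesis tests.

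The conclusion rests on reading the cell by the convention of its neighbours and by the protocol's own definition of QID. It applies to protocol Version 4.1. It should be corrected because it is a contradictory safety limit in the operative dosing table and costs almost nothing to remove.

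**What to change.** In the Week 8 cell of the Protocol 5.5.1 table, restate the ceiling as 1 mg QID (4 mg total daily dose). This follows the format of the other three dose cells and agrees with every other current statement. Section 9.1.8 needs no change, because its overdose definition refers to the prespecified total daily dose and will have a single value once the cell is corrected.

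SAP Section 4 refers to protocol v5.0, so check first whether the cell survives in that version. If it does, correct it there and tell sites.

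The cost is one table cell, plus a short site notice if the error is still in force.

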5.5.2 Dose Adjustment

The oral levosimendan dose may be decreased in 1 mg increments or interrupted as clinically warranted if the subject has hypotension, tachycardia, or signs or symptoms consistent with hypovolemia (e.g., low SBP, decreasing urine output with rising blood urea nitrogen [BUN] and serum creatinine). Record the date of discontinuation or down titration. Patients should be monitored closely until clinically stable.

Missed doses should be skipped and not taken as a double dose at the next dosing time.

Refer to the following subsections for additional guidance on events that require study drug discontinuation or dosage adjustment, permanent discontinuation, and re-initiating study drug in subjects in whom clinical stability has been restored.

5.5.3 Dose-limiting Events

Dose limiting cardiac events and instructions are detailed in [Attachment 3 Cardiac Event Recommendations and Management](#). In addition to these events, the dose may be adjusted at any time the physician judges that it is in the best interest of the patient to reduce the dose or discontinue levosimendan.

5.5.4 Storage

Study drug (levosimendan capsules) must be stored at room temperature.

The Sponsor must be notified upon discovery of any excursion. Temperature excursions will require site investigation as to cause and remediation. Tenax will determine the ultimate impact of excursions on the investigational product and will provide supporting documentation as necessary. Under no circumstances should product be dispensed to/consumed by subjects until the impact is determined and product is deemed appropriate for use.

